#### 4.0 STUDY DESIGN

Open-label, dose escalation study of 24 subjects with advanced dry-[AMD](#) and [GA](#) divided into four cohorts ([Figure 1](#)):

##### Cohorts 1 – 3

The first 2 cohorts, consisted of 3 eyes of 3 legally blind subjects with best corrected visual acuity of 20/200 or less in the study eye, all received a single subretinal implantation of OpRegen.

The third cohort included 6 eyes of 6 subjects with best corrected visual acuity of 20/200 or less in the study eye, all received a single subretinal implantation of OpRegen.

Staggered intervals and safety data review by the independent data safety monitoring board ([DSMB](#)) occurred within and between cohorts to ensure subjects safety and welfare.

##### Cohort 4

The fourth cohort included 12 eyes from 12 subjects with [BCVA](#) between 20/64 and 20/250 in the study eye, all received a single subretinal targeted implantation of OpRegen.

Staggered intervals and safety data review by the [DSMB](#) occurred between at least the first two subjects of each delivery modality to ensure subject safety and welfare.

[figure not shown]

### All Cohorts

The study is being conducted in participants with confirmed bilateral [GA](#) (Study Eye and Non-Study, Fellow Eye).

**Figure 1. Protocol Enrollment Schema**

## 4.1 Definitions

### 4.1.1 Study Day and Study Reference Period

Time will be measured as Study Day defined according to Clinical Data Interchange Standards Consortium (CDISC) standard. That is, the date of the OpRegen injection is [REDACTED]. The date before the OpRegen injection is [REDACTED]. Study day can be calculated as follows:

Study Day = visit date – date of OpRegen injection

Last study day for a subject is the subject’s last clinical visit date recorded on the subject status [eCRF](#). If this date is missing for a subject, the last date found in the clinical database (e.g., clinical lab test date or date of vital sign collection) will be used as the last study date for the subject.

Total days on study are the total number of days a subject has been followed up after OpRegen injection. Mathematically it can be calculated as follows:

Total days on study = last study date – date of OpRegen injection + 1

#### 4.1.2 Baseline and Change from Baseline

Unless indicated otherwise, change from baseline (CFB) will be calculated as follows, where the baseline assessment is the last assessment before OpRegen injection:

$$\text{CFB} = \text{Value at Visit} - \text{Baseline}$$

Percent change from baseline (PCFB) will be calculated as follow:

$$\text{PCFB (\%)} = 100 * (\text{Value at Visit} - \text{Baseline}) / \text{Baseline}$$

## 5.0 STUDY POPULATION

Subject characteristics, numbers, and all inclusion and exclusion criteria are described in Protocol Section 8.

## 6.0 STATISTICAL ANALYSIS GENERAL CONSIDERATIONS

The planned sample size of 24 treated eyes, [REDACTED], with targeted doses of  $50 \times 10^3$  and up to  $200 \times 10^5$  cells, is considered clinically appropriate for further characterization of the safety, tolerability, and preliminary efficacy of OpRegen in the treatment of subjects with advanced dry-form [AMD](#) with [GA](#).

Comprehensive interim reports of accumulated safety, tolerability and preliminary available efficacy data were presented to the [DSMB](#) prior to escalation to the next to come study dose and to enrolment of the next to come study cohort. Between cohorts, and subjects when applicable, the next step to proceed occurred per [DSMB](#) recommendation based on accumulated safety data.

All measured variables and derived parameters will be listed individually and if appropriate, presented in summary tables by dose regimen group and overall, providing sample size, absolute and relative frequency for categorical variables, or sample size, arithmetic mean, standard deviation, median, minimum, and maximum for continuous variables. [Confidence intervals](#) will be presented for the efficacy endpoints for exploratory purposes only. Complete analyses to be prospectively performed are outlined in this SAP.

### 6.1 Analysis Sets

#### All Treated Population

The All Treated Population will include all subjects who received OpRegen. This will be used for all safety and efficacy analyses.

#### Per Protocol (PP) Analysis Set

The Per Protocol (PP) analysis set is a subset of the All Treated Analysis Set and will consist of all subjects who received the OpRegen implantation and violated none of the major protocol guidelines.

## 6.2 Significance Level

Though no formal hypothesis testing was originally planned for this study, for purposes of this SAP, a significance level of 0.05 using two-tailed tests will be utilized for any exploratory significance testing performed.

## 6.3 Procedures for Handling Missing Data and Outliers

Missing or incomplete dates will be imputed per [Section 4.1.1](#) for the purposes of determining treatment emergence. All other missing data will not be imputed, unless otherwise noted.

All unscheduled visit data will be included in data listings. In the data summary tables, the presence of missing data will be indicated by the inclusion of a 'missing' category with categorical data, and a count and percentage of missing observations for continuous numeric data, where applicable.

## 6.4 Descriptive Statistics

All measured variables and derived parameters will be listed individually and if appropriate, presented in summary tables by dose regimen group and overall, providing sample size, absolute and relative frequency for categorical variables, or sample size, arithmetic mean, standard deviation, median, minimum, and maximum for continuous variables. [Confidence intervals](#) will be presented for the efficacy endpoints for exploratory purposes only.

## 7.0 STATISTICAL METHODS

All data collected for this study will be presented in summary tables, listings, and figures (TLFs) as indicated in [Section 11](#) of this SAP. Shells for TLFs with enough detail for programming will be provided as a guide to develop the programming SAS codes. These shells will be in sufficient detail to simulate the actual TLFs when they are created from the locked database.

Tabulations for continuous data will use a standard set of summary statistics: number of observations available (n), mean, standard deviation ([SD](#)), median, and range (minimum, maximum).

Categorical or dichotomous data will be tabulated using counts and percentages. The numerator and denominator for each percentage calculation will be specified in the footnotes of table shells.

Data listings will present all information recorded in [eCRFs](#) and any derived variable(s) included in the analysis datasets for all subjects and visits.

For the SAP primary hypothesis, the dose will be defined to exceed the maximally tolerated dose ([MTD](#)) if at least two of the subjects in a cohort have [DLT](#).

If the dose has not exceeded the [MTD](#) in Cohort 1, the study will proceed to Cohort 2, pending the [DSMB](#) review. If the dose has not exceeded the [MTD](#) in Cohort 2, the study will proceed to Cohort 3, pending the [DSMB](#) review of data from Cohorts 1 and 2. Enrollment of Cohort 4, using either method of surgical delivery, will proceed only after review of the accumulated safety data by the [DSMB](#).

For the SAP secondary hypothesis concerning changes in retinal structure and function following OpRegen implantation, the small number of subjects (3 per cohort in Cohorts 1 and 2, up to 6 in

Cohort 3 and approximately 12 in Cohort 4) precludes any definitive assessment of change through formal statistical testing. However, the following data analytical techniques will be used to describe the retinal structure and function results: assessing the changes in treated eyes will involve comparing the magnitude of observed changes in retinal structure and function to the distribution of changes between visits in a given subject (including historical data, when available), and will be also compared to the same measures gathered from previously studied populations of similarly affected subjects.

Measurements of retinal structure and function made on the non-treated eye of each subject will also be examined in the same way as for the treated eye to evaluate the extent to which placebo effects or unexpected temporal trends may be contributing to observed changes in retinal function.

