22.14 STATISTICAL METHODS

For the primary hypothesis the dose will be defined to exceed the maximally tolerated dose (MTD) if at least two of the subjects in a cohort have DLT.

If the dose has not exceeded the MTD in Cohort 1, the study will proceed to Cohort 2, pending the DSMB review. If the dose has not exceeded the MTD in Cohort 2, the study will proceed to Cohort 3, pending the DSMB review of data from Cohorts 1 and 2. Enrollment of Cohort 4 will proceed only after review of the accumulated safety data by the DSMB.

For the secondary hypothesis concerning changes in retinal structure and function following OpRegen[®] implantation, the small number of subjects (3 per cohort in Cohorts 1 and 2, up to 6 in Cohort 3 and approximately 12 in Cohort 4) precludes any definitive assessment of change through formal statistical testing. However, the following data analytical techniques will be used to describe the retinal structure and function results: assessing the changes in treated eyes will involve comparing the magnitude of observed changes in retinal structure and function to the distribution of changes between visits in a given subject (including historical data, when available), and will be also compared to the same measures gathered from previously studied populations of similarly affected subjects.

Measurements of retinal structure and function made on the non-treated eye of each subject will also be examined in the same way as for the treated eye to evaluate the extent to which placebo effects or unexpected temporal trends may be contributing to observed changes in retinal function. The non-treated eyes form a good comparison group for the fellow treated eyes in terms of rate of enlargement of GA.

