### 3.3 Study Hypothesis

As this is an open label, phase I/IIa dose escalation, safety, tolerability, and preliminary efficacy study, neither power assessment, nor formal hypotheses testing were planned for study outcome measures. However, for purposes of data analyses and this SAP, the Sponsor hypothesizes that implantation of OpRegen to subjects with advanced dry-form AMD with GA is safe, well-tolerated and provides evidence of preliminary efficacy based on pre-specified functional and structural assessments.

The primary hypothesis is that there will be no dose-limiting toxicity (DLT) and that implantation of OpRegen to subjects with progressive dry-form AMD with GA will be safe and well-tolerated. For this study DLT is defined as an SAE determined to be product related.

A secondary null hypothesis is that there will be no difference in disease progression, as measured by retinal function and structure, between the treated and untreated regions in the treated eye and between the treated and untreated eye of a subject.

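### A treated eye's change is described against the same subject's between-visit changes, with no matching of interval and no limit to pre-implantation visits

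*SAP*

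**What the plan says.** The secondary hypothesis (SAP 3.3, Protocol 22.13) is that progression does not differ between treated and untreated regions of the treated eye, or between the treated and untreated eye.

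For this hypothesis SAP 7.0 rules out definitive testing because the cohorts are small. It offers a descriptive method instead: "comparing the magnitude of observed changes in retinal structure and function to the distribution of changes between visits in a given subject". A subject's historical data join that reference only if there are any, and a further comparison is made with earlier study populations. Protocol 22.14 uses the same wording: "assessing the changes in treated eyes will involve comparing the magnitude of observed changes in retinal structure and function to the distribution of changes".

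On the fellow eye, SAP 7.0 has a sentence that begins "Measurements of retinal structure and function made on the non-treated eye of each subject will also be examined in the same way as for the" and goes on to name the implanted eye. The stated purpose there is to pick up placebo effects or time trends in retinal function. Protocol 22.14 goes one step further: "The non-treated eyes form a good comparison group for the fellow treated eyes in terms of rate of enlargement of GA". The SAP does not carry that sentence.

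Three other places bear on the point:

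- SAP 4.1.2 defines change from baseline, "where the baseline assessment is the last assessment before OpRegen injection".
- SAP 8.0 plans a treated or fellow eye column in the summary tables.
- SAP 11.0 lists a figure and a listing for the GA annual rate. It gives no formula for the rate, and no output is titled for the within-subject comparison or for a paired difference between eyes.

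**The concern.** A change from baseline is the sum of the between-visit changes that lead up to it. Setting that sum against the distribution of its parts is not a like-for-like comparison, and the bias runs in opposite directions for structure and function.

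- **GA area.** The lesion is expected to grow. A year's growth is many times one interval's growth, so an eye that grows exactly as it would have done untreated can still stand out.
- **BCVA.** A post-operative drop and recovery are two large between-visit changes. If they enter the reference, they widen it, and a lasting loss looks unremarkable.
- **Both.** Any effect of the product is itself part of the reference.

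The secondary question is whether OpRegen alters progression. A description that makes usual growth look unusual, or real loss look usual, can mislead the reader of the study report even though no test is done.

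**Working it through.** **Inputs.** The documents give no GA growth rate, reading SD, BCVA test SD, size of post-operative dip or cut-off, and the visit dates are redacted. There is therefore no planned figure to reproduce. From the documents: about 52 weeks in Part 1 (Protocol synopsis) and 12 on-site visits after the procedure (Protocol 11.3.2.5). Assumed: 12 equal intervals, linear growth, independent reading errors, and a change called unusual if it lies outside 1.96 SD of the eye's own 12 steps. The 1.96 SD rule is only a device for measuring the distortion; the plan does not contain it.

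**GA, no treatment effect.** Let growth be g per year and reading SD be σ.

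- 12-month change: mean g, SD √2·σ.
- Mean step: g/12.
- Expected variance of the 12 steps about their mean: 2σ²·(12 − 1/12)/11 = 2.167σ², so the SD is about 1.47σ.
- For g = 1.5 mm² and σ = 0.2 mm²: mean step 0.125, step SD about 0.29, upper limit about 0.125 + 1.96 × 0.29 = 0.70 mm². The 12-month change centres on 1.5 with SD 0.28, far above that limit.

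Simulation (20,000 eyes per setting, mean ± 1.96 SD rule) gives the share of unchanged-growth eyes outside the limits:

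| Growth, mm²/year | σ = 0.1 | σ = 0.2 | σ = 0.3 |
|---|---|---|---|
| 1.0 | 100% | 89% | 58% |
| 1.5 | 100% | over 99% | 88% |
| 2.0 | 100% | 100% | 98% |

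The share falls with slower growth or more noise. Adding two pre-implantation visits and letting σ reach 0.8 mm², it is 25% at 1.5 mm²/year and 7% at 0.5 mm²/year. Unequal spacing hardly matters: at 1.5 mm²/year with σ of 0.3 and 0.5 mm², an unequal schedule gives 88% and 51%, an equal one 89% and 52%. The driver is a cumulative change set against single steps.

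**BCVA.** Assume test SD 5 letters, a true 15-letter loss at the last visit, and a 20-letter dip at the first post-operative visit, all inside the reference.

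- Noise part of the step variance: 2.167 × 25 = 54.2.
- Loss part: one step of −15, mean step −1.25, so (225 − 12 × 1.25²)/11 = 206.25/11 = 18.75.
- Dip part: steps of −20 and +20, so (400 + 400)/11 = 72.7.
- Cut-off without the dip: 1.96 × √(54.2 + 18.75) = 16.7 letters. With the dip: 1.96 × √(54.2 + 18.75 + 72.7) = 23.7 letters. The simulated average cut-offs are 16.3 and 23.2, slightly lower because an average of SDs lies below the root of the average variance.

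The 15-letter loss is flagged in 36% (limits centred on the mean step) to 44% (centred on zero) of eyes without the dip, and in 6% to 11% with it.

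**Matched alternative.** The treated-minus-fellow GA change between the same two dates has mean 0 if both eyes grow at the same average rate, and SD √4·σ = 2σ from reading error. Judged against the SD of that difference, 5% of eyes fall outside 1.96 SD at every growth rate tried (0.5, 1.5 and 2.5 mm²/year). This is so by construction, because the common growth cancels.

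**The case against.** The strongest reply is that the text contains none of this explicitly. The method is descriptive. SAP 3.3 says "neither power assessment, nor formal hypotheses testing were planned for study outcome measures", and the level in SAP 6.2 ("a significance level of 0.05 using two-tailed tests will be utilized for any exploratory significance testing performed") is not tied to this comparison. No cut-off exists, so nothing is formally called changed. That stands, and it is why the percentages are illustrations, not error rates of the plan.

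A reader might also infer that the plan pools unequal intervals and includes recovery visits. The documents do not say so. They leave both open, and the dates are redacted. Historical data are expressly allowed, though only when available, which leaves study visits as the default reference.

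Nor is this the only yardstick. Past populations and the fellow eye are named, and ordinary growth would show in the fellow eye too. That is a real safeguard, but a partial one. The fellow eye is put through the same within-subject comparison, the past populations are not identified, and a column per eye is not a paired difference.

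Finally, a 3-line loss would not go unseen. BCVA change is summarised and listed (SAP 7.1.10 and 11.0), and BCVA is a safety endpoint in Protocol 7.3.1. What could go wrong is how such a loss is interpreted against the reference.

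**Conclusion.** The point holds as a defect in a stated descriptive method. The reference distribution is undefined, and on the natural reading (change from baseline against between-visit changes) it is a poor yardstick for a progressive lesion and, if recovery visits count, for BCVA. Under the assumptions above, 58% to 100% of eyes with unchanged GA growth would look extreme, and a 20-letter dip would cut the flagging of a 15-letter BCVA loss from about 36–44% to 6–11%.

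Two stronger readings are not supported. Ordinary growth would not always stand out: the share drops to 7% with slow growth and noisy readings. Vision loss would not always be masked: a sizeable dip must occur and must be in the reference. Nor can one say that the trial is unable to address progression, since the fellow-eye data are planned. What is missing is a specified paired comparison that uses them.

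**What to change.** Replace the sentence in SAP 7.0 and Protocol 22.14 with three elements.

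1. **Main descriptive comparison.** Use the within-subject treated-minus-fellow change between the same two dates, for GA annual rate and BCVA, with a confidence interval. SAP 6.4 already foresees exploratory intervals for efficacy endpoints. Restore in the SAP the Protocol 22.14 sentence on fellow eyes as the GA growth comparator, define the annual rate, and add the output to SAP 11.0.
2. **Own history.** Where earlier images exist, compare annualised growth after implantation with the same eye's annualised growth before it.
3. **Measurement noise.** For BCVA, FAF and SD-OCT, estimate it only from the two pre-implantation assessments (screening and the pre-surgical visit in Protocol 11.3.1), pooled over subjects. Keep post-operative visits out of it.

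The cost is document wording and a little programming, with no new data. SAP 2.0 allows revision before database lock. There are limits. The noise estimate rests on few repeats. The pre-surgical visit does not list microperimetry, so retinal sensitivity is not covered. The study eye is the worse eye, so the fellow eye may differ at baseline, and the two baseline values should be shown beside each paired difference. The treated-versus-untreated-region part of the hypothesis is not addressed by this change.

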11.3.2.4 Surgical Procedure and Implantation of OpRegen®

The eye chosen for OpRegen® implantation will be the eye with worse visual acuity. The surgery will be performed by retro-bulbar or peribulbar anesthetic block or monitored intravenous sedation or by general anesthesia, at the discretion of the surgeon and in discussion with the subject. The eye undergoing surgery will be prepped and draped in sterile fashion according to the institutional protocol.

OpRegen® Subretinal Implantation with Vitrectomy

Vitrectomy procedure is required in the majority of cases in which retinal or sub-retinal intervention is performed. It is a routine procedure, with a low incidence of complications. The procedure involves formation of three small sclerotomies, removal of the vitreous gel, and then immediate implantation of the OpRegen® into the subretinal space via a very small caliber cannula.

The subretinal implantation as described following vitrectomy is schematically depicted in [Figure 3](#)²³ below.

[figure not shown]

Figure 3: Subretinal Implantation After Vitrectomy

A surgical procedure manual describes the details of the procedures for vitrectomy and OpRegen® subretinal implantation.

[figure not shown]
²³ From ([Stout JT 2011](#)). (Note that in this schematic drawing, placement of the surgical ports is not anatomically accurate).

Detailed surgical procedure manuals provided to the sites describe the specifics of the individual procedures. All surgical implantation procedures will be video-recorded for subsequent analyses.

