20.2 DATA SAFETY MONITORING BOARD

The DSMB will be composed of independent physicians with expertise in ophthalmology/clinical trials in the targeted population, and a statistician. A DSMB Charter specifying role, process, and constitution of the DSMB will be prepared and signed by all members. The DSMB will receive safety data of each study cohort periodically, carefully review it and forward to the Sponsor its recommendations regarding study continuation. It will have the right to recommend discontinuation of the trial for safety reasons or for overwhelming clinical effect.

The DSMB members will communicate with the Sponsor with regards to issues resulting from the conduct and clinical aspects of the trial. The Sponsor will work closely with the board to provide the necessary data for review.

The justification for lack of sponsor blinding of the data provided to the DSMB is based on the fact that the study is an open label and single-arm design; therefore, safety monitoring is of major importance.

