**Table 1. Study Assessments**

Assessment	Time points	Primary Endpoints/ Safety	Efficacy Endpoints of Clinical Relevance
Best-Corrected Visual Acuity (BCVA)-ETDRS Retro illuminated 4-meter ETDRS Chart “R” for refraction followed by Chart “1” and “2” BCVA is reported in number of letters read correctly. First, the right eye is tested with Chart 1 and then the left eye is tested with Chart 2. Must be conducted by trained examiner (technician acceptable) and as per “BCVA Instructions Manual”.	[REDACTED]	√	√
Low Luminance Best Corrected Visual Acuity LL BCVA is measured by placing a 2.0-log-unit neutral density filter over the trial frame in front of the study eye and having the participant read the normally illuminated ETDRS chart using a different version of the chart. This test is optional as subjects with low vision will not be able to perform this test and is not applicable for Cohorts 1-3.	[REDACTED]		√
Spectral Domain Optical Coherence Tomography (SD-OCT) Images obtained by certified examiner (technician acceptable). Reading of images done by central reading center. Refer to Central Reading manual for instructions.	[REDACTED]	√	√
[REDACTED]	[REDACTED]	√	
Dilated Fundus Examination (peripheral retina, macula, choroid, optic nerve, retinal/detachment, retinal or vitreous hemorrhage, vitreous hemorrhage density, vitreous cells.)	[REDACTED]	√	

Assessment	Time points	Primary Endpoints/ Safety	Efficacy Endpoints of Clinical Relevance
Microperimetry Automated microperimetry to be performed in Cohort 3 (optional) and in Cohort 4. Must be conducted by certified examiner (technician is acceptable). Reading of images done by central reading center. Refer to Central Reading manual for instructions.		√	√
Fluorescein Angiography (FA) Standard procedure for detection of CNV . Must be conducted by certified examiner (technician is acceptable): at [REDACTED] to verify dry AMD and absence of neovascular (wet) AMD , and on final exam at end of study; optional FA during follow-up in cases of suspected conversion to wet AMD		√	
Intraocular Pressure (IOP) One IOP measurement per eye		√	
Slit Lamp Examination (Lids/Lashes, Conjunctiva, Cornea, Iris, Aqueous Cells, Aqueous Flare and Lens) Must be conducted by certified examiner (technician is acceptable)		√	

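### The fellow eye can show only effects common to both eyes; it cannot measure placebo or examiner effects specific to the operated eye, as Protocol 22.14 and SAP 7.0 imply

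*SAP*

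**What the plan says.** In Protocol 22.14 the relevant sentence begins "Measurements of retinal structure and function made on the non-treated eye of each subject will also be examined in the same way as for the"; the comparison is with the operated eye. SAP 7.0 repeats the sentence. Both give the same purpose: "to evaluate the extent to which placebo effects or unexpected temporal trends may be contributing to observed changes in retinal function".

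The setting is described elsewhere:

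- Protocol 20.2 says that "the study is an open label and single-arm design". SAP 4.0 has "Open-label, dose escalation study of 24 subjects".
- Protocol 11.3.2.4 fixes which eye is operated: "The eye chosen for OpRegen® implantation will be the eye with worse visual acuity". No sham procedure is described for the other eye.
- Protocol 22.14 goes on to say: "The non-treated eyes form a good comparison group for the fellow treated eyes in terms of rate of enlargement of GA". That endorsement concerns a structural measure only. The SAP keeps the placebo sentence about function but does not carry this one over.
- SAP 3.3 hypothesizes that the implantation "provides evidence of preliminary efficacy based on pre-specified functional and structural assessments". Its secondary null hypothesis compares the treated with the untreated eye on function as well as structure.
- SAP Table 1 describes low-luminance BCVA as "placing a 2.0-log-unit neutral density filter over the trial frame in front of the study eye".

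**The concern.** To evaluate how far placebo contributes to a functional change, a comparator must be exposed to the same expectation without the treatment. The fellow eye is not. The subject knows which eye had surgery, and so does the site. Hope of benefit, extra effort on the chart and encouragement from the examiner can all be directed at that eye. BCVA is a count of letters read by the subject, so it responds to effort.

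The functional half of the efficacy conclusion is at stake. BCVA and low-luminance BCVA are among the efficacy analyses in SAP 7.1.10. SAP 8.0 gives summary tables a column for treated or fellow eye, so readers will see the contrast. SAP 6.2 allows exploratory tests at 0.05. Protocol 6.2 says the Cohort 4 efficacy results may inform later studies. If the sentence stands, the report can say that placebo was evaluated when the component most relevant to unilateral surgery was not.

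**Working it through.** **The plan's own figures.** The documents give no effect size, power or estimator for the fellow-eye comparison, so there is nothing to reproduce beyond the total of 3 + 3 + 6 + 12 = 24 eyes. The question is what the comparison can identify.

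**Step 1: what each eye's change contains.** Let T be the time trend common to both eyes, g the practice, general effort or placebo effect common to both, e the expectation, effort or examiner effect specific to the operated eye, and τ the true product effect.

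- Treated-eye change = T + g + e + τ
- Fellow-eye change = T + g
- Treated minus fellow = e + τ

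The fellow-eye change does not contain e, so it carries no information on e. The difference contains e and τ only as a sum, so it cannot separate them. Even the shared part appears only as the total T + g: an unchanged fellow eye is also what a decline offset by shared practice or effort would produce.

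**Step 2: if placebo is partly shared.** Let the total placebo effect in the treated eye be P, with a fraction s also acting on the fellow eye. The fellow eye then shows T + sP, and the difference carries (1 − s)P + τ. The bias is the full P at s = 0 and disappears at s = 1. Nothing in the documents fixes s or P.

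**Step 3: illustration.** Simulation with n = 12 pairs (the Cohort 4 size), τ = 0, no shared trend or shared effect, 20,000 runs per setting and two-sided 95% t intervals. Assumed, not from the documents: SD of BCVA change 5 or 8 letters, between-eye correlation 0.3 or 0.6, and e = 0, 3, 5 or 8 letters. Ranges are over the four SD and correlation settings.

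| e (letters) | Mean fellow-eye change | Fellow-eye CI covers 0 | Mean treated minus fellow | CI for difference wholly above 0 |
|---|---|---|---|---|
| 0 | −0.01 to 0.01 | 94.9–95.1% | −0.01 to 0.02 | 2.4–2.5% |
| 3 | −0.01 to 0.03 | 94.6–95.2% | 2.98 to 3.00 | 16.9–56.0% |
| 5 | −0.02 to 0.01 | 94.9–95.2% | 4.99 to 5.01 | 38.3–93.9% |
| 8 | −0.02 to 0.00 | 94.9–95.0% | 7.99 to 8.01 | 76.2–100% |

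A fellow eye compatible with no change is as likely at e = 8 as at e = 0, while the between-eye difference tracks e. The table illustrates Step 1. It is not evidence that e takes any of these values.

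**Step 4: the other comparisons in SAP 7.0.** Treated-eye changes are also to be set against visit-to-visit variation within the subject and against earlier groups with similar disease. Neither is described as having a matched expectation of benefit, so neither removes e.

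**Step 5: low-luminance BCVA.** The description in both Table 1s places the filter before the study eye only. As described there is no fellow-eye value, so not even the shared component can be examined for this endpoint.

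**The case against.** The strongest reply is that the sentence is hedged and descriptive. It speaks of what may be contributing, and it pairs placebo with temporal trends, which the fellow eye can address. The plan disclaims formal testing, calls its confidence intervals exploratory and says the numbers are too small for a firm conclusion. It specifies no estimator for the between-eye difference; the listed BCVA endpoints are changes from baseline. Examiner masking could be set out in the BCVA manual or in redacted text. Microperimetry is automated and centrally read, so examiner encouragement is a weaker route there.

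Much of this stands, and it rules out several stronger readings that a reader might infer:

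- *That the plan would declare placebo excluded if the fellow eye is flat.* Neither document says so. It is only a natural use of the stated purpose.
- *That the fellow eye says nothing about placebo.* It can reveal a component common to both eyes, although mixed with the time trend.
- *That functional results are overstated by a particular number of letters.* Any such number is assumed, and assuming an effect in one eye only builds in the answer.
- *That NEI VFQ-25 and FRI break the promise to examine both eyes alike.* The sentence covers measurements made on the non-treated eye; subject-level questionnaires are not among them.
- *That structural measures must therefore carry more weight.* That is a preference, and masking of the central readers to the treated eye is not stated either.

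The caveats do not answer the central point. Small numbers limit precision, whereas this is a bias that more subjects would not reduce. Masked examiners would remove one route, but the subject would still know which eye was operated.

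**Conclusion.** The point holds in this limited form. Both documents give the fellow eye a property that the design does not provide: it can speak to effects common to both eyes, but not to expectation, effort or examiner effects specific to the operated eye. The bias in a treated-minus-fellow functional contrast equals that eye-specific component, whose size cannot be derived from the documents.

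The conclusion rests on three features of the plan: open-label treatment, surgery on one known eye, and no sham described. It does not depend on the assumed SDs, correlations or letter values. It applies to effort-dependent measures such as BCVA and is much weaker for GA area. Leaving temporal trends within the fellow eye's role is sound.

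**What to change.** In Protocol 22.14 and SAP 7.0, replace the phrase that names placebo effects and unexpected temporal trends with: *temporal trends, test-learning and other effects common to both eyes*.

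Then add: *Because treatment is open-label and unilateral, fellow-eye data do not estimate placebo or examiner effects specific to the treated eye. An unchanged fellow eye will not be used to attribute functional change to the product.*

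Also note in both places that low-luminance BCVA, as described, is measured in the study eye only and has no fellow-eye comparator.

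The change needs no new data or analyses, so it remains possible even though the SAP describes all 24 subjects as already treated. The downside is a more modest claim for the functional results.
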